7.3.1.4. Beta-Lactamase Production

- Variables: Beta-lactamase production (Positive/Negative)
- Analysis: Beta-lactamase production by specimen source (urogenital, pharyngeal, and rectal) will be summarized by visit for Micro-ITT, Micro-ITT Rectal, Micro-ITT Pharyngeal Population. A listing for beta-lactamase production will be provided.

7.3.1.5. NAAT outcome and response

- Variables: NAAT outcome and response will be determined by pathogen (NG or Mgen), body site (as applicable), for the TOC and FU visits as follows:
 - Those participants who have NG detected from their baseline NAAT specimen (urogenital, pharyngeal, rectal) will be evaluated for NAAT outcome and response at TOC visit for urogenital, pharyngeal, rectal respectively. For baseline pharyngeal NG confirmed participants, NAAT specimen will be evaluated at follow up visit as well if both the baseline and TOC pharyngeal NAATs were positive. Participants who have Mgen nucleic acid detected from their baseline NAAT specimen will be evaluated for Mgen NAAT outcome and response at follow up visit. The NAAT outcome and

response to study treatment will be determined by prespecified programmed algorithm for each participant (see Table 3).

- The NAAT outcome will be determined by comparing the baseline NAAT result with the respective NAAT result at each subsequent visit. The corresponding NAAT response (success or failure) by participant will then be assigned. The criteria for determining NAAT outcome and response are shown in Table 3 and Table 4.
- Participants who are a NAAT failure at the TOC visit but have not switched to other systemic antimicrobials with activity against NG are evaluable at FU visit (applicable to pharyngeal NG only).
- Participants who received other systemic antimicrobials on or after the TOC visit will be categorized as Unable to determine for NAAT outcome or response at the FU visit.

Table 3 NAAT Outcome and Response at the TOC Visit (NG Only)

Defining Criteria	NAAT Outcome	NAAT Response
Clearance of baseline pathogen nucleic acid from a specimen taken at the TOC visit, without the participant receiving other systemic antimicrobials before this visit	Nucleic acid clearance	NAAT success
Persistence of baseline pathogen nucleic acid from a specimen taken at the TOC visit, without the participant receiving other systemic antimicrobials before this visit	Nucleic acid persistence	NAAT failure ^a
1) A determination of the nucleic acid outcome from a specimen taken at the TOC visit cannot be made (e.g., no sample taken, sample lost, visit did not occur) 2) The participant received other systemic antimicrobials before the TOC visit	Unable to determine	NAAT failure ^a

NAAT=Nucleic Acid Amplification Test; NG=*Neisseria gonorrhoeae*; TOC = Test-of-Cure.

Note: Specimen refers to either a urogenital, pharyngeal, or rectal specimen obtained for NAAT. The NAAT outcomes are determined on a per-pathogen and per-specimen source basis.

- a. Participants who are a “NAAT failure” at the TOC visit assessment yet are not switched to other systemic antimicrobials are evaluable at subsequent time points.

Table 4 NAAT Outcome and Response at the FU Visit (Pharyngeal NG and Urogenital Mgen Only)

Defining Criteria	Microbiological Outcome	Microbiological Response
Clearance of baseline pathogen nucleic acid from a specimen taken at the FU visit, without the participant receiving other systemic antimicrobials before this visit	Nucleic acid clearance	NAAT success
Persistence of baseline pathogen nucleic acid from a specimen taken at the FU visit, without the participant receiving other systemic antimicrobials before this visit	Nucleic acid persistence	NAAT failure
A determination of the nucleic acid outcome from a specimen taken at the Follow-up Visit cannot be made (e.g., no sample taken, sample lost, visit did not occur) Note: Any participants who received other systemic antimicrobials before the Follow-up Visit will not be evaluated for NAAT outcome or response at the Follow-up Visit	Unable to determine	NAAT failure

Mgen=*Mycoplasma genitalium*; NAAT=Nucleic Acid Amplification Test; NG=*Neisseria gonorrhoeae*.

Note: Specimen refers to either a urogenital or pharyngeal specimen obtained for NAAT. The NAAT outcomes are determined on a per-pathogen and per-specimen source basis and will only be conducted if either the Baseline (NG or Mgen) and TOC (NG only) NAAT assay showed the presence of nucleic acid for the respective pathogen and specimen.

Note: Participants who are a “NAAT failure” at the TOC visit assessment yet are not switched to other systemic antimicrobials are evaluable at subsequent time points.

- Analyses: NAAT results (outcome and response) will be summarized by visit for each body site as indicated in the table below. Summaries for NAAT outcome at the TOC visit will be based on the 95% Exact (Clopper-Pearson) CIs for each treatment group. For urogenital body site at the TOC visit, the adjusted (adjusting for actual pooled strata of sex and sexual orientation) estimates of the difference in NAAT success rate for the two treatments (gepotidacin – ceftriaxone plus azithromycin) with 2-sided 95% CI using MN method. For the body sites pharyngeal and rectal, unadjusted estimates of difference in NAAT success rate for the two treatments and CIs will be presented. Analyses based on the FU visit (Pharyngeal NG and Urogenital Mgen) will also use this unadjusted approach since it is anticipated that there will be insufficient observations to adequately perform an adjusted analysis. A listing of NAAT results will also be provided. NG phenotype and genotype results will appear in summary tables, listings, and figures. Summary by strata and stratification combinations defined in Section 5.4.1. will also be reported. For each stratum, the percent of participants with NAAT successes by treatment group and unadjusted difference in percent between treatment groups with corresponding two-sided 95% CI using MN method will be reported. Treatment group differences will be displayed for subgroups with ≥ 10 participants across both treatment groups. The table below outlines planned analyses for NAAT outcome and response:

Analysis/Endpoint Description	Visit	Body site	Population	Subgroup
NAAT outcome and response rate for NG	TOC	Urogenital Rectal Pharyngeal	micro-ITT, micro-ITT Rectal, micro-ITT Pharyngeal	
	TOC	Urogenital Rectal Pharyngeal	micro-ITT, micro-ITT Rectal, micro-ITT Pharyngeal	Subgroup categories defined in Section 5.4.2 Strata and Stratification combination defined in Section 5.4.1
	TOC	Urogenital Rectal Pharyngeal	ME, ME Rectal, ME Pharyngeal	
	TOC	Urogenital Rectal Pharyngeal	ME, ME Rectal, ME Pharyngeal	Subgroup categories defined in Section 5.4.2 Strata and Stratification combination defined in Section 5.4.1
	TOC	Urogenital Rectal Pharyngeal	ME NAAT TOC, ME NAAT TOC Rectal, ME NAAT TOC Pharyngeal	
	TOC	Urogenital Rectal Pharyngeal	ME NAAT TOC, ME NAAT TOC Rectal, ME NAAT TOC Pharyngeal	Subgroup categories defined in Section 5.4.2 Strata and Stratification combination defined in Section 5.4.1

Analysis/Endpoint Description	Visit	Body site	Population	Subgroup
NAAT outcome and response rate for NG	FU	Pharyngeal	micro-ITT Pharyngeal	
	FU	Pharyngeal	ME NAAT FU Pharyngeal	
NAAT outcome and response rate for Mgen	FU	Urogenital	micro-ITT	
	FU	Urogenital	ME NAAT FU Mgen	

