4. OBJECTIVES AND ESTIMANDS/ENDPOINTS

Objectives	Endpoints

Primary
 
 To evaluate the efficacy of oral gepotidacin compared to IM ceftriaxone plus oral azithromycin to treat participants with uncomplicated urogenital gonorrhea caused by NG 	
 Culture-confirmed bacterial eradication of NG from the urogenital body site (i.e., microbiological success) at the TOC (Day 4 to 8) Visit

Secondary
 
 To evaluate the efficacy of oral gepotidacin compared to IM ceftriaxone plus oral azithromycin to treat participants with rectal gonorrhea caused by NG To evaluate the efficacy of oral gepotidacin compared to IM ceftriaxone plus oral azithromycin to treat participants with pharyngeal gonorrhea caused by NG To evaluate the safety and tolerability of oral gepotidacin compared to IM ceftriaxone plus oral azithromycin 	
 Culture-confirmed bacterial eradication of NG from the rectal body site (i.e., microbiological success) at the TOC (Day 4 to 8) Visit Culture-confirmed bacterial eradication of NG from the pharyngeal body site (i.e., microbiological success) at the TOC (Day 4 to 8) Visit Treatment-emergent AEs and serious AEs (SAEs) and change from baseline results for clinical laboratory tests and vital sign measurements

Exploratory
 
 To assess the clearance or persistence of NG nucleic acid (by nucleic acid amplification test [NAAT] assay) from urogenital specimens for oral gepotidacin compared to IM ceftriaxone plus oral azithromycin To assess the clearance or persistence of NG nucleic acid (NAAT assay) from pharyngeal specimens for oral gepotidacin compared to IM ceftriaxone plus oral azithromycin 	
 Urogenital NG NAAT results at the TOC (Day 4 to 8) Visit Pharyngeal NG NAAT results at the TOC (Day 4 to 8) and Follow-up (Day 14 to 21) Visits, where only participants who did not receive other systemic antimicrobials at or after the TOC (Day 4 to 8) Visit will be evaluated at the Follow-up Visit

 To assess the clearance or persistence of NG nucleic acid (NAAT assay) from rectal specimens for oral gepotidacin compared to IM ceftriaxone plus oral azithromycin 	
 Rectal NG NAAT results at the TOC (Day 4 to 8) Visit

Objectives	Endpoints

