9.1.2. NAAT Assay

Refer to the laboratory manual for local versus central laboratory details and the number and type of specimens to collect for NAAT assay. See Table 2 for collection of NAAT assay samples.

Pretreatment urogenital specimens will be obtained from all participants for NAAT assay to detect the presence of NG, Mgen, and CT nucleic acids at the Baseline Visit. Urogenital specimens will also be obtained from all participants for NAAT assay to detect the presence of NG and CT nucleic acids at the TOC Visit. At the Follow-up Visit, a urogenital specimen for NAAT assay will be collected for detection of Mgen only from participants who had a positive NAAT assay for Mgen at Baseline.

In addition, pretreatment baseline pharyngeal and rectal specimens for NAAT assay for detection of NG and CT will be obtained from participants who are willing to provide such specimens, regardless of known exposure. Specimens will also be collected for NAAT assay for detection of NG and CT at the TOC Visit from all body sites collected at the Baseline Visit. At the Follow-up Visit, a pharyngeal specimen for NAAT assay will be collected for detection of NG and CT from participants whose NAAT assay had the presence of nucleic acid for NG at **both** Baseline and TOC.

The NAAT assay will be performed at a designated laboratory(ies). Participants testing positive for CT or Mgen nucleic acid by NAAT assay at the Baseline Visit should be treated per local standard of care at or after the TOC Visit or at the Follow-up Visit (if treatment has not already been initiated), as required, after all study procedures for the visit have been completed.

Only those participants who have NG or Mgen nucleic acid detected from their baseline NAAT specimen will be evaluated for NAAT outcome and response. The NAAT outcome and response to study treatment will be determined by an algorithm at GSK before breaking of the study blind (**Note:** Sponsor is blinded to participant treatment assignment; see Section 7.4).

For the exploratory objectives, the NAAT outcome is determined by comparing the baseline NAAT result with the respective NAAT result at each subsequent visit. The corresponding NAAT response (success or failure) “by participant” will then be assigned, as shown in Table 6 and Table 7.

Table 6 Determining NAAT Outcome and Response at the Test-of-Cure Visit (NG Only)

Defining Criteria	NAAT Outcome	NAAT Response

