Clearance of baseline pathogen nucleic acid from a specimen taken at the TOC Visit, without the participant receiving other systemic antimicrobials before this visit	Nucleic acid clearance	NAAT success
Persistence of baseline pathogen nucleic acid from a specimen taken at the TOC Visit, without the participant receiving other systemic antimicrobials before this visit	Nucleic acid persistence	NAAT failure ^a
1) A determination of the nucleic acid outcome from a specimen taken at the TOC Visit cannot be made (e.g., no sample taken, sample lost, visit did not occur) 2) The participant received other systemic antimicrobials before the TOC Visit	Unable to determine	NAAT failure ^a

NAAT=nucleic acid amplification test; NG=*Neisseria gonorrhoeae*; TOC = Test-of-Cure.

Note: Specimen refers to either a urogenital, pharyngeal, or rectal specimen obtained for NAAT. The NAAT outcomes are determined on a per-pathogen basis.

a. Participants who are a “NAAT failure” at the TOC Visit assessment yet are not switched to other systemic antimicrobials are evaluable at subsequent time points.

Table 7 Determining NAAT Outcome and Response at the Follow-Up Visit (Pharyngeal NG and Mgen Only)

Defining Criteria	NAAT Outcome	NAAT Response
Clearance of baseline pathogen nucleic acid from a specimen taken at the Follow-up Visit, without the participant receiving other systemic antimicrobials before this visit	Nucleic acid clearance	NAAT success
Persistence of baseline pathogen nucleic acid from a specimen taken at the Follow-up Visit, without the participant receiving other systemic antimicrobials before this visit	Nucleic acid persistence	NAAT failure
A determination of the nucleic acid outcome from a specimen taken at the Follow-up Visit cannot be made (e.g., no sample taken, sample lost, visit did not occur) Note: Any participants who received other systemic antimicrobials before the Follow-up Visit will not be evaluated for NAAT outcome or response at the Follow-up Visit	Unable to determine	NAAT failure

Mgen=*Mycoplasma genitalium*; NAAT=nucleic acid amplification test; NG=*Neisseria gonorrhoeae*.

Note: Specimen refers to either a urogenital or pharyngeal specimen obtained for NAAT. The NAAT outcomes are determined on a per-pathogen basis and will only be conducted if both the Baseline (NG and Mgen) and TOC (NG only) NAAT assay showed the presence of nucleic acid for the respective pathogen and specimen.

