ME NAAT TOC Pharyngeal Population	
 Participants who meet the definition of the Micro-ITT Pharyngeal Population and follow important components of the study and were NG NAAT positive for Pharyngeal specimen at baseline (i.e., (1) receive all planned doses as randomized and actual treatment is the same as randomized, (2) have a Pharyngeal NAAT specimen collected at the TOC Visit, with available NAAT results, (3) have not taken any other systemic antibiotic prior to TOC, unless it was taken for the current infection, and (4) have no major deviation that prevents evaluation of efficacy). Participants will be analyzed according to their randomized treatment arm. 	
 Efficacy
ME NAAT FU Mgen Population	
 Participants who meet the definition of the Micro-ITT and follow important components of the study and were Mgen (urogenital) NAAT positive at baseline (i.e., (1) receive all planned doses as randomized and actual treatment is the same as randomized, (2) have Mgen (urogenital) NAAT specimen collected at 	
 Efficacy

Population	Definition / Criteria	Analyses Evaluated
	
the FU Visit, with available NAAT results, (3) have not taken any other systemic antibiotic prior to FU, unless it was taken for the current infection, and (4) have no major deviation that prevents evaluation of efficacy).
 
 Participants will be analyzed according to their randomized treatment arm. 	
ME NAAT FU Pharyngeal Population	
 Participants who meet the definition of the Micro-ITT Pharyngeal Population and follow important components of the study and were NG (pharyngeal) NAAT positive at baseline and TOC (i.e., (1) receive all planned doses as randomized and actual treatment is the same as randomized, (2) have a NG (pharyngeal) NAAT specimen collected at the FU Visit, with available NAAT results, (3) have not taken any other systemic antibiotic prior to FU, unless it was taken for the current infection, and (4) have no major deviation that prevents evaluation of efficacy). Participants will be analyzed according to their randomized treatment arm. 	
 Efficacy

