- k. At Follow-up, a pharyngeal specimen will be collected for detection of NG and CT by NAAT from participants whose NAAT assay had the presence of nucleic acid for NG at both Baseline and TOC. NAAT assay results will be available to the study sites by the Follow-up Visit.

Table 7 BTZ116577 NAAT Overview by Body Site and Organism

Body site	Organism	Baseline Visit			TOC Visit		F/U Visit	
		Local Lab	Central Lab		Central Lab		Central Lab	
			Real Time	Batch	Real Time	Batch	Real Time	Batch
Urogenital	NG/CT	X	X		X			
	MGen			X				X ^b
Pharyngeal ^a	NG/CT		X		X		X ^c	
Rectal ^a	NG/CT		X		X			

NG = *N. gonorrhoeae*; CT = *C. trachomatis*; MGen = *M. genitalium*; RT = real time (processed upon arrival); F/U=Follow-up.

a. Optional (upon patient consent)

b. Only if positive NAAT at baseline visit. MG NAATs will be run weekly by the central lab, so that baseline and results are back to the site in time for F/U.

c. Only if positive NG NAAT at baseline and TOC visit. Sites will have baseline and TOC pharyngeal NAAT results back by F/U

Note: Only central laboratory NAAT results will be used in the exploratory analysis, local lab NAAT is conducted to guide therapy at the TOC visit (*Chlamydia trachomatis*)

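### The planned Follow-up difference in pharyngeal NG NAAT success is taken only among participants still positive at TOC, so it does not compare randomised groups and can favour the slower-clearing arm (minor; exploratory endpoint)

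*SAP*

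**What the plan says.** Protocol Section 4 lists an exploratory objective, "To assess the clearance or persistence of NG nucleic acid (NAAT assay) from pharyngeal specimens for oral gepotidacin compared to IM ceftriaxone plus oral azithromycin", with NAAT results at TOC and at Follow-up as the endpoint.

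Who contributes at Follow-up is set in several places:

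- SAP 7.3.1.5: the "NAAT specimen will be evaluated at follow up visit as well if both the baseline and TOC pharyngeal NAATs were positive".
- SAP Section 4, ME NAAT FU Pharyngeal Population: participants who "were NG (pharyngeal) NAAT positive at baseline and TOC".
- SAP 12.1.1, Table 6 notes: the Follow-up pharyngeal specimen is taken only "from participants whose NAAT assay had the presence of nucleic acid for NG at both Baseline and TOC".
- Protocol 9.1.2, note to Table 7: Follow-up outcomes "will only be conducted if both the Baseline (NG and Mgen) and TOC (NG only) NAAT assay showed the presence of nucleic acid".
- SAP 7.3.1.5, note to Table 4, the counterpart of Protocol Table 7: outcomes "will only be conducted if either the Baseline (NG or Mgen) and TOC (NG only) NAAT assay showed the presence of nucleic acid".

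For the analysis, SAP 7.3.1.5 gives pharyngeal and rectal sites an unadjusted difference in NAAT success with a CI, and adds: "Analyses based on the FU visit (Pharyngeal NG and Urogenital Mgen) will also use this unadjusted approach". The reason given is the small number of observations expected. The planned-analysis table lists two populations for Follow-up pharyngeal NG: micro-ITT Pharyngeal and ME NAAT FU Pharyngeal. SAP 7.3 and 7.3.3 make all exploratory analyses descriptive, with no formal testing.

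**The concern.** TOC NAAT status is measured after randomisation and is the exploratory outcome at the TOC visit. Selecting on it breaks the balance that randomisation provides. An arm that clears most participants quickly enters Follow-up with a small, hard-to-clear remainder. An arm that clears slowly enters with a larger group that still includes people about to clear. The planned Follow-up success rate is then the chance of late clearance among persisters, which is a different quantity from clearance by Day 14 to 21, and its between-arm difference has no straightforward causal reading.

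The SAP gives no caveat about this selection and plans no measure of clearance by either visit over everyone who was positive at Baseline. What is at stake is how one exploratory display would be read: a reader could take a positive difference as evidence of better pharyngeal clearance when it reflects slower clearance by TOC.

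**Working it through.** **Inputs.** The documents give no pharyngeal NAAT clearance rate for either arm, so there is no planned figure to reproduce. All clearance figures below are assumptions, and no relapse is assumed.

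**Formulae.** In one arm, let *n* be baseline pharyngeal NAAT-positive, *a* cleared at TOC, and *b* of the remaining *n* − *a* cleared at Follow-up.

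- Planned Follow-up rate: *b* / (*n* − *a*).
- Clearance by either visit: (*a* + *b*) / *n*.

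As proportions, with T cleared by TOC and F cleared by Follow-up, the planned rate is (F − T) / (1 − T) and clearance by either visit is F.

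**Worked example (assumed counts, 20 per arm).** Gepotidacin: *a* = 10, *b* = 8. Comparator: *a* = 16, *b* = 2. Differences are gepotidacin minus comparator.

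- At TOC: 10/20 = 50% against 16/20 = 80%; difference −30 points.
- Planned Follow-up: 8/10 = 80% against 2/4 = 50%; difference +30 points.
- Cleared by either visit: 18/20 = 90% against 18/20 = 90%; difference 0.

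**Range (assumed rates).** A is the faster arm at TOC; differences are A − B.

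| A: T, F | B: T, F | Planned rates, A v B | Planned A − B | Either-visit A − B |
|---|---|---|---|---|
| 80%, 90% | 50%, 90% | 50% v 80% | −30 | 0 |
| 80%, 90% | 50%, 85% | 50% v 70% | −20 | +5 |
| 80%, 90% | 60%, 85% | 50% v 62.5% | −12.5 | +5 |
| 80%, 90% | 50%, 80% | 50% v 60% | −10 | +10 |
| 80%, 90% | 50%, 75% | 50% v 50% | 0 | +15 |
| 80%, 95% | 50%, 85% | 75% v 70% | +5 | +10 |
| 80%, 96% | 50%, 75% | 80% v 50% | +30 | +21 |

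The last row has a constant clearance chance in each interval (80% and 50%), so F = 1 − 0.2² = 96% and 1 − 0.5² = 75%. In rows 2 to 4 the sign reverses. In row 1 a difference appears where there is none, and in row 5 a real one disappears. In the last two rows the direction is right but the size is not. With T at 80% and 50%, the arms enter Follow-up with 20 and 50 participants per 100 baseline-positive, which shows how unlike the two groups are.

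**The case against.** The strongest reply is that nothing is decided on this result. It is exploratory, any CI is descriptive, and the benefit/risk plot in SAP Section 10 uses only urogenital endpoints at TOC. The Follow-up sample is a deliberate second look at persisters, described consistently in the sampling rules, and whether late positives resolve is a fair question. The numbers will be small: for 8/10 against 2/4, an unstratified Miettinen-Nurminen interval runs from roughly 20 points below zero to just over 70 above, so the display would itself show how little it says. All of that stands and limits the severity. It does not make a difference between groups selected on outcome interpretable, and the SAP gives sparse data, not selection, as its reason for the unadjusted method.

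A reader might infer more than the documents support:

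- *That the pharyngeal NAAT objective cannot be answered.* The TOC comparison does not condition on the TOC result, so that part is intact.
- *That participants who cleared at TOC will be scored as failures because no Follow-up specimen exists.* Table 4 does score an absent specimen as failure, its note says *either* where Protocol Table 7 says *both*, and the micro-ITT Pharyngeal row does not state its denominator. On that reading the example becomes 8/20 = 40% against 2/20 = 10%. But the operative sentence in SAP 7.3.1.5 requires both NAATs to be positive, so this is an ambiguity to close and not the plan.
- *That the bias is certain, or favours gepotidacin.* Neither follows. The direction depends on which arm clears faster by TOC, which the documents do not say.

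**Conclusion.** The point holds as a minor one. The planned Follow-up difference in pharyngeal NG NAAT success is conditional on a post-randomisation treatment result, so it is not a comparison of randomised groups, and it can but need not favour the arm that clears more slowly. In the worked example the planned figure is +30 points against a difference of 0 in clearance by either visit. Across the assumed rates above, the planned figure ranged from 30 points too low to 9 points too high for the faster arm (−30 against 0; +30 against +21). These are illustrations that rest on assumed clearance rates and no relapse, not estimates of the bias in this trial. The TOC pharyngeal NAAT comparison and the primary and secondary culture endpoints are unaffected.

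**What to change.** 1. **TOC-positive subset.** In SAP 7.3.1.5 and Tables 2.338 and 2.339, show for each arm the number entering and the number cleared at Follow-up for pharyngeal NG. Drop the between-arm difference and its CI.

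2. **If a Follow-up comparison is wanted,** add an endpoint of clearance at TOC, or at Follow-up for those still positive at TOC. Use all baseline pharyngeal NAAT-positive participants in the micro-ITT Pharyngeal Population as the denominator.
   - Take TOC clearance from SAP Table 3, so that antimicrobials given after a TOC clearance do not change it.
   - Keep TOC-positive participants who receive other systemic antimicrobials before Follow-up in the denominator under one stated rule. SAP 7.3.1.5 now makes them unable to determine, which is a failure under Table 4, while the Table 4 note leaves them unevaluated. These must be reconciled.
   - State that TOC-negative participants are not resampled. The abstinence or condom requirement in Protocol 6.3 ends at TOC, so relapse or re-infection afterwards would go unseen.

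3. **Wording.** State the denominator of the micro-ITT Pharyngeal Follow-up row in the planned-analysis table, change *either* to *both* in the Table 4 note to match Protocol Table 7, and record any added endpoint in SAP 2.1, which now reports no changes from the protocol.

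The cost is SAP text and, if the second step is taken, one derived variable from data already collected. No new samples or visits are needed. The real price is the untestable assumption that participants cleared at TOC stay clear.

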To assess the clearance or persistence of Mycoplasma genitalium (Mgen) nucleic acid (by NAAT assay) from urogenital specimens for oral gepotidacin compared to IM ceftriaxone plus oral azithromycin	Urogenital Mgen NAAT results at the Follow-up (Day 14 to 21) Visit, where only participants who did not receive other systemic antimicrobials at or after the TOC (Day 4 to 8) Visit will be evaluated
To evaluate the microbiological characteristics and antimicrobial susceptibility profile of NG from urogenital, pharyngeal, or rectal specimens	Gram stain (urogenital specimens only), bacterial culture, and in vitro susceptibility test results from urogenital, pharyngeal, or rectal specimens at the Baseline (Day 1), TOC (Day 4 to 8), and Follow-up (Day 14 to 21), as data permits

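### The SAP gives conflicting rules for follow-up NAAT outcomes after other systemic antimicrobials: failure, not evaluated, or still evaluable

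*SAP*

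**What the plan says.** The follow-up NAAT endpoints are exploratory. SAP 7.3.1.5 plans an unadjusted between-arm difference with a CI, in the micro-ITT sets and in two ME follow-up sets. Four treatments of participants who took other systemic antimicrobials can be found:

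- **Undetermined, hence failure.** A bullet in SAP 7.3.1.5: "Participants who received other systemic antimicrobials on or after the TOC visit will be categorized as Unable to determine for NAAT outcome or response". In Table 4, *Unable to determine* is an outcome whose response is NAAT failure. The row is defined by "A determination of the nucleic acid outcome from a specimen taken at the Follow-up Visit cannot be made", and its examples are missing samples or visits.
- **Not evaluated.** A note in that same row: "Any participants who received other systemic antimicrobials before the Follow-up Visit will not be evaluated for NAAT outcome or response at the Follow-up Visit". Protocol Table 7 carries the same note. The endpoint definitions (protocol Section 4, SAP 2.2) agree; for *M. genitalium* the SAP wording is "where only participants who did not receive other systemic antimicrobials at or after the TOC (Day 4 to 8) Visit will be evaluated".
- **Evaluable unless the drug is NG-active.** Another bullet, limited to pharyngeal NG, says that TOC failures who "have not switched to other systemic antimicrobials with activity against NG are evaluable at FU visit". The footnote to Table 4 drops the activity qualifier: "yet are not switched to other systemic antimicrobials are evaluable at subsequent time points".
- **Kept in the population.** In SAP Section 4, the ME NAAT FU Mgen and ME NAAT FU Pharyngeal populations require that participants "3) have not taken any other systemic antibiotic prior to FU, unless it was taken for the current infection".

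SAP 2.1 declares no change from the protocol's planned analyses, so no passage is marked as overriding another.

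**The concern.** The response is to be assigned by a programmed algorithm, and one algorithm cannot carry out all four rules. The rules put the same person in the numerator, in the denominator only, or in neither.

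Other antimicrobial use between TOC and follow-up is expected, because the protocol has participants with chlamydia or *M. genitalium* treated at or after TOC. It may also differ by arm. Only the comparator contains azithromycin, which protocol 5.4 describes as effective for chlamydia. If gepotidacin participants receive more post-TOC treatment, a failure rule counts that against gepotidacin whatever the study drug did.

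**Working it through.** **1. The rules applied to the same people**

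| Participant | 7.3.1.5 bullets | Table 4 note, protocol Table 7 | ME follow-up definition |
|---|---|---|---|
| Pharyngeal NG, NAAT-positive at baseline and TOC, then given a drug without NG activity for another condition | One bullet: evaluable. Next bullet: undetermined, so failure | Not evaluated | Excluded |
| Same, but given therapy for the current gonorrhea after TOC | Undetermined, so failure | Not evaluated | Kept |
| *M. genitalium* positive, treated at the follow-up visit after the specimen was taken | Undetermined, so failure (no upper time limit) | Evaluated (use was not before the visit) | Kept |

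In the second row, the clearance and persistence rows of Table 4 both require no other antimicrobials before the visit. A participant kept in the ME set under the current-infection exception therefore fits neither.

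**2. The time window**

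The 7.3.1.5 bullet and the endpoint definitions start at TOC and have no end. The Table 4 note and the ME definitions end at follow-up and have no start.

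**3. Effect on the difference**

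The documents give no follow-up clearance rate, no rate of antimicrobial use and no expected number for these analyses, so there is no planned figure to reproduce. Every rate below is an assumption.

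Let *c* be clearance in non-users, equal in both arms, and *u*G and *u*C the share of users on gepotidacin and comparator.

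- Users as failures: rate = *c*(1 − *u*), so difference = −*c*(*u*G − *u*C).
- Users not evaluated: rate = *c* in each arm, so difference = 0, provided use is unrelated to clearance.
- Users analysed as observed, with clearance *c*u: difference = (*u*G − *u*C)(*c*u − *c*).

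With *c* = 80% and use of 20% versus 10%:

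- Failure rule: 0.80 × 0.80 = 64% versus 0.80 × 0.90 = 72%, a difference of −8 points.
- Not evaluated: 80% versus 80%, a difference of 0.
- As observed, with *c*u = 95%: 0.10 × 0.15 = +1.5 points.

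Difference in points under the failure rule over a range of assumptions:

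| Clearance | Use 20% vs 20% | 10% vs 5% | 20% vs 10% | 30% vs 10% |
|---|---|---|---|---|
| 50% | 0 | −2.5 | −5 | −10 |
| 80% | 0 | −4 | −8 | −16 |
| 90% | 0 | −4.5 | −9 | −18 |

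A 10-point shift needs a use imbalance of 0.10/*c*: 20 points at 50% clearance, 12.5 at 80% and 11.1 at 90%.

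**4. Precision**

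Assume 50 per arm, 80% clearance and use of 30% versus 10%. The failure rule gives 28/50 versus 36/50, −16.0 points (Miettinen-Nurminen 95% CI −33.9 to 2.9). Not evaluated gives 28/35 versus 36/45, 0.0 (−18.8 to 17.5). The point estimate depends on the rule, but both intervals are wide.

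**The case against.** The best defence is that the documents, read together, point to one rule. The SAP's TOC table (Table 3) lists antimicrobial use as a route to failure. Its follow-up table does not, and carries an exclusion note instead. The protocol is consistent on not evaluating users. The conflicting bullet calls the response undetermined as well as the outcome, and does not itself say failure. This stands as an argument for which rule to keep. It does not remove the conflict, because Table 4 has no undetermined response and attaches failure to that category.

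It can also be said that the ME definitions set membership, not outcome, and that the current-infection exception appears in every ME population. That is correct. The difficulty is that it retains people to whom Table 4 can assign neither clearance nor persistence.

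On size, the objection largely succeeds. The instruction to treat co-infections covers both arms, as required, with no comparator exemption. SAP Appendix 1 times the baseline *M. genitalium* results to reach sites for follow-up, which limits treatment directed at that organism before the follow-up specimen. A higher rate of use on gepotidacin is plausible through chlamydia treatment, but it is an inference.

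Nor is non-evaluation free of bias. It drops participants given alternative therapy after persistence at TOC, which can flatter the arm with more persistence.

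**Conclusion.** The inconsistency is real and lies in the SAP. As written, it leaves the follow-up NAAT denominators, and so the differences, dependent on which sentence is programmed. The shift between the failure and not-evaluated rules is −*c*(*u*G − *u*C), for example −8 points at the assumed 80% clearance and 20% versus 10% use. With equal use there is no artefact. The zero under non-evaluation rests on use being unrelated to clearance.

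Two stronger readings are not supported. A reader might infer that the choice of rule will produce a large between-arm difference. The documents give no usage or clearance rates, so a large difference is only a possibility. A reader might also infer that the pharyngeal follow-up comparison should be rebuilt, because only participants positive at both baseline and TOC are resampled. That sampling rule is explicit in the protocol, and choosing another estimator for a descriptive summary is a separate matter.

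The consequence is limited. SAP 7.3 plans no formal testing and offers CIs for description only. Few follow-up observations are expected, and the benefit/risk plot uses urogenital NAAT at TOC. The primary analysis, type I error and power are unaffected.

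**What to change.** Apply the protocol endpoint rule throughout: users of other systemic antimicrobials are not evaluated at follow-up. Use one window, at or after TOC and before the follow-up specimen is taken.

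- **SAP 7.3.1.5:** replace the undetermined bullet and remove the NG-activity qualifier. State the same window in Table 4.
- **SAP Section 4:** align the two ME NAAT FU populations by removing the current-infection exception for this window.
- **Use before TOC only:** say how these participants are handled, since the Table 4 rows exclude them and the endpoint wording does not.
- **Reporting:** give the number of users excluded per arm, and show users-as-failures as a sensitivity summary, because exclusion also removes participants given alternative therapy after persistence at TOC.

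If the sponsor prefers a different rule, SAP 2.1 should declare it as a change from the protocol.

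The cost is SAP wording, one derivation and one extra summary. The downside is smaller evaluable numbers in analyses already expected to be small, and possible selection from excluding treated failures.
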